## **2.1 Primary Objectives**

The primary objectives of this efficacy trial are to:

- 1) test the efficacy of the TCBD intervention compared to usual care for improving primary outcomes [i.e., size-appropriate restraint (dichotomous) and the Child Passenger Safety Score (CPaSS) (numeric)] assessed at 12 months
- 2) use latent growth curve models to identify characteristic trajectories for the CPaSS observed in digital photographs submitted to the study team by caregivers over the 12 study months.

Correlates of the trajectory types will be assessed

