## **3.3 Study Measures**

Over the course of this study, participants will complete the following surveys: screen, baseline, 6- and 12-month survey. At the 6-month follow-up, the participants will also complete a brief health literacy assessment called the Newest Vital Sign.

The selected measures for the surveys are reliable, valid, and have been pilot tested in the study population. Measures will be assessed at screening, baseline and re-assessed at the 6- and 12-month follow-up visits. Assessments will be self-administered or RC facilitated on a study iPad in the ED and at in-person follow-up assessments (Months 6 and 12). Skip patterns will reduce administration time. Our team has found baseline assessment lasting 20 minutes to be feasible and acceptable to caregivers in the ED setting during pilot testing.

Table 1 illustrates survey measures for this study along with the frequency/timing of assessments.

Table 1: Measures	Assessment Month(s)
OUTCOMES	
Primary Outcome	
Size Appropriate Restraint Use (dichotomous)	6 and 12
Child Passenger Safety Score direct observation	6 and 12
Secondary Outcome	
Child Passenger Safety Score remote observation	ED/Baseline through 12
Exploratory Cost Measures	
Intervention Time (ED, Phone MI) for RA/Counselor	ED/Baseline and 2
Intervention Time (ED, Phone MI, texts, web app) for caregiver	ED/Baseline through 12
Material Costs - iPads, computers, maintenance	ED/Baseline through 12
Intervention Costs - Photograph review, texts, web app	ED/Baseline through 12
MODERATORS/MEDIATORS	
Caregiver Demographic Characteristics, reason for ED visit	ED/Baseline
Child Size	

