# Emergency Medicine Prospective Protocol

## 5 Study Procedures

### 5.1 Study Intervention or Observational Phase

#### 5.1.1 Visit 1 (baseline visit)

Screening: Caregivers of children who are eligible to approach will complete a self-administered computerized screening survey on a study iPad or remotely via their own personal device to determine eligibility for the full study.

Caregivers who complete the screening survey and meet study eligibility requirements will have the option to enroll in the full study. Eligible caregivers will participate in the informed consent process before determining if they would like to enroll.

Eligible caregivers that enroll in the study will complete the following elements while in the ED or will have the option to finish any of these elements within 5 business days of enrollment remotely via phone.

- A self-administer a computerized baseline survey with validated items collecting information on their child passenger safety practices with their child, barriers/challenges they may experience in using the recommended child restraint, and motivations, etc.
- Tiny Cargo check-in (a car seat check) with the RA to directly observe and record how their child normally rides in a vehicle. We will use the CPaSS tool to collect data during the Tiny Cargo check-in. Caregiver can submit photos during remote recruitment.
- Randomization to the basic TCBD intervention (an ED counseling session plus eHealth after ED discharge) or the control condition (usual ED care with discharge instructions relevant to the child's diagnosis and an information sheet about car safety).
- Caregivers within the TCBD intervention group --Brief motivational interviewing inspired counseling session (~20 minutes).

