## 6 Statistical Plan

### 6.1 Sample Size and Power Determination

Briefly, our calculations are based on two-sample comparisons between groups (e.g., control and TCBD) using results from our pilot study that assessed percent size-appropriate child passenger safety behaviors at 6-month follow-up (referred to as the “response rate” below). For analyses involving multiple time points, these calculations represent a conservative lower bound on the power that would only be achieved if the effective sample equals 1 observation per person (i.e. perfect within-individual correlation). For the calculations below we assume: a) 17% response rate among controls; b) 25% response rate among TCBD caregivers at 6 Month (with 75% of TCBD caregivers re-randomized); and c) only 80% of the target sample (n=204 controls and n=516 TCBD in the initial dichotomy) will be available for analysis at follow-up. Components (a) and (b) are based on pilot data where the control group received generic educational materials and outcomes were assessed at 6-months. Component (c) is a conservative correction for attrition. For Aim 2, we estimated power while accounting for uncertainty in the group sizes by simulating response and re-randomization patterns according to the above probabilities and testing for significant between-group differences; this process was repeated 10,000 times and the power was estimated as the percent of replications in which a between-group difference was identified. Binary Outcome: For the binary response case, if the observed response rate is at least 29.4% among those receiving enhanced TCBD, it can be reliably (>80% power) distinguished from a control response rate of 17%. Analogously, a response rate of at least 27.6% among basic intervention would be reliably (>80% power) distinguished from control. Converted to Cohen's  $h$ , both differences reflect small-to-medium effect sizes ( $h = 0.30$  and  $h = 0.26$ , respectively). Numeric Outcome (CPaSS): If the standardized mean difference (i.e. Cohen's  $D$ ) is  $>0.25$  (a small-to-medium effect size), we can reliably distinguish between control and basic TCBD conditions. Similarly, if  $D \geq 0.28$ , a small-to-medium effect size, we will have sufficient power (80%) to distinguish the control and enhanced TCBD conditions. Aim 2: Monte Carlo studies of linear latent trajectory models indicate that a medium level of heterogeneity among the slopes and/or intercepts of the trajectories can be reliably recovered (power  $> 80\%$ ) with a total sample size of  $n=200$ , with power exceeding 95% when the level of heterogeneity is high; given that our sample size soundly exceeds 200, we expect sufficient ability to determine the underlying characteristic trajectory types. Nevertheless, we further justify our sample size with a brief simulation study. Assuming a final sample size of 720, conservatively assuming individuals are only measured at an average of 25% of the 12 monthly assessments, we simulate data from a population with four equally likely trajectory types: consistently low, consistently high, linearly decreasing, and starting high then dropping off. Because we have no basis for estimating variability in the score, we assumed mean/variance equivalence, consistent with the Poisson distribution. Due to the time required to fit such models, we only completed 200 simulation replications, where we were able to correctly conclude (based on BIC) that there were four

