## 6.2 Statistical Methods

All subjects, once randomized, will be included in an intention-to-treat analysis and outcomes will be collected even if the caregiver does not engage in the randomly assigned intervention. We will evaluate randomization by testing for covariate (e.g. demographic characteristics) balance between initial treatment groups, and between the re-randomized treatment groups created after the 6-month follow-up. If significant differences are observed, we will adjust for these variables or conduct stratified analyses. All statistical hypothesis tests and power calculations will use a two-sided = 0.05.

**Aim 1:** To test the efficacy of the TCBD intervention compared to usual care for improving primary outcomes [i.e., size-appropriate restraint (dichotomous) and CPaSS (numeric)] at 12 months. We hypothesize greater proportions of children will be using a size-appropriate restraint and higher CPaSS among caregivers in the intervention groups (basic and enhanced) compared with the control group (usual care) at the 12-month assessment. **Statistical Analysis:** Our primary analytic tool for estimating treatment effects will be generalized linear models (GLMs), and for analyses involving joint analysis of multiple follow-up data points, we will use generalized linear mixed models (GLMMs), which allows direct modeling of the correlations between data points (e.g. repeated measurements on individuals), and the inclusion of individuals with incomplete data (e.g. missing time points). The GLM(M) framework also allows simple controlling for confounders (if necessary) through their inclusion in the model as covariates. For the analysis of binary outcomes, we will use logistic GLM(M)s and for numeric outcomes (CPaSS-D) we will initially specify linear (Gaussian) GLM(M)s; this choice will be scrutinized by analyzing model diagnostics. The primary inferential target will be the coefficient for the treatment group indicator, making this effectively equivalent to ANCOVA. Adjustment for the baseline measurement is important for guarding

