# Emergency Medicine Prospective Protocol

against regression to the mean in RCT studies, which will be our approach when analyzing only a single follow-up (e.g. 12 months). However, when analyzing multiple follow-ups within the same model, using this baseline adjustment across the board (i.e. at every time point) can result in overestimation of the treatment effect; baseline adjustment for only the first follow-up corrects this overestimation while also guarding against regression to the mean, which will be our approach. We will also conduct exploratory tests of the interaction between time and treatment group, to see whether there is strong evidence that the treatment effect diminishes over time, which will inform future studies.

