**Aim 2:** To use latent growth curve models to identify characteristic trajectories for the CPaSS observed in digital photographs over the 12 study months and assess for correlates of the trajectory types. We hypothesize that caregivers will have different CPaSS trajectories in response to the basic intervention, the enhanced intervention, and the control condition. We expect to identify at least four patterns of response. **Statistical Analysis:** We will determine 12-month CPaSS trajectory types using adaptations of finite mixture models for the case where the units are trajectories. We will define trajectory shapes through methods combining semiparametric regression modeling (e.g., generalized additive models), with latent class regression, using the R package flexmix. Following convention, we will use the Bayesian Information Criteria (BIC) to determine the appropriate number of latent classes, while also making practical considerations to avoid overfitting, such as not allowing overly small groups to be created, as in previous applied work. Using the posterior probability of class membership, we place individuals into trajectory groups and treat that grouping as the outcome in a subsequent multinomial regression model to determine correlates of class membership, including treatment group, caregiver race/ethnicity, and child age group. If substantial uncertainty in class membership is found, outcomes in the multinomial model will be weighted accordingly.

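### The Aim 2 model of CPaSS trajectory class does not name baseline CPaSS as a covariate, and the plan leaves open whether baseline belongs to the trajectory itself

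*Combined protocol and SAP*

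**What the plan says.** Section 6.2, Aim 2, hypothesises that CPaSS trajectories differ between basic TCBD, enhanced TCBD and control. Each caregiver is assigned to a latent trajectory class. Class is then the outcome of a multinomial regression used "to determine correlates of class membership, including treatment group, caregiver race/ethnicity, and child age group".

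Baseline CPaSS is collected. Section 5.1.1 says of the baseline visit: "We will use the CPaSS tool to collect data during the Tiny Cargo check-in". In 3.3, Table 1 lists "Child Passenger Safety Score remote observation" from the ED/baseline assessment through Month 12. Sections 3.2 and 3.4.1 instead start the trajectory photographs at Month 1.

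For Aim 1, section 6.2 treats baseline adjustment as important for guarding "against regression to the mean in RCT studies, which will be our approach when analyzing only a single follow-up". It limits the adjustment to the first follow-up when several follow-ups are modelled jointly. Nothing comparable is written for Aim 2.

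On status, 2.1 lists as a primary objective to "use latent growth curve models to identify characteristic trajectories for the CPaSS observed in digital photographs", with correlates of class added afterwards. Sections 3.2, 3.3 (Table 1) and 3.4.1 call the trajectory a secondary outcome.

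**The concern.** Baseline CPaSS is the same instrument as the outcome. Of the four trajectory types assumed in 6.1, two are defined by level alone (steadily low and steadily high) and a third by a high start. Baseline is therefore a plausible strong predictor of class. Leaving a strong predictor out of a logistic-type model puts its variation into the unexplained part and weakens the test of treatment.

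What is at stake is power for the Aim 2 treatment comparison, and clarity about which treatment odds ratios are the main result. With an open covariate list, that choice could be made after the data are seen.

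**Working it through.** **Inputs**
- Test level: "All statistical hypothesis tests and power calculations will use a two-sided = 0.05" (6.2).
- Analysable sample: "only 80% of the target sample (n=204 controls and n=516 TCBD in the initial dichotomy) will be available for analysis at follow-up" (6.1), that is 720 in total. The 3:1 ratio in 3.2 would give 720/4 = 180 controls and 540 TCBD. Both splits are used below.
- Re-randomised share: "25% response rate among TCBD caregivers at 6 Month (with 75% of TCBD caregivers re-randomized" (6.1). 0.75 × 516 = 387. Split 1:1, this gives 193.5 enhanced and 129 + 193.5 = 322.5 basic.
- Correlation ρ between baseline CPaSS and trajectory level: not in the documents. Assumed 0.5, range 0.3 to 0.7.
- Share of caregivers with a pre-randomisation score: not in the documents. Assumed all, half or a quarter.

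**Step 1. The plan's own figures.** For numeric CPaSS, 6.1 gives 80% power at D = 0.25 (basic v control) and D = 0.28 (enhanced v control). With power = Φ(D/√(1/n₁ + 1/n₂) − 1.96):
- Basic: 0.25/√(1/204 + 1/322.5) = 0.25/0.0895 = 2.795; Φ(0.835) = 79.8%.
- Enhanced: 0.28/√(1/204 + 1/193.5) = 0.28/0.1003 = 2.790; Φ(0.830) = 79.7%.

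Both reproduce. Neither concerns trajectory class. Section 6.1 attaches the Aim 2 label to a simulation of between-group differences, but the results it reports are for restraint use and mean CPaSS. Its trajectory simulation checks recovery of the number and shape of classes. No power is stated for treatment in the class model.

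**Step 2. Linear benchmark.** For a mean, baseline adjustment multiplies the SD by √(1 − ρ²), which is 0.866 at ρ = 0.5. Basic v control becomes Φ(2.795/0.866 − 1.96) = Φ(1.267) = 89.7%, a gain of 9.9 points. At ρ = 0.3 the gain is 3.6 points and at 0.7 it is 17.7. This shows the mechanism; it is not the class model.

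**Step 3. The class model.** Simulated 3-df likelihood-ratio test for treatment in a four-class multinomial logit, without and with baseline. Classes are treated as known and TCBD is one group.
- *Level A*: four ordered classes cut from one score correlated ρ with baseline; treatment shifts the score.
- *Level B*: outer quarters are the low and high classes, the middle half is split at random into two declining shapes; treatment shift 0.31.
- *Change*: treatment acts only on a change component unrelated to baseline.

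| Model | Control/TCBD | Shift | ρ | Without | With | Gain (points) |
|---|---|---|---|---|---|---|
| Level A | 204/516 | 0.25 | 0.5 | 63.5% | 76.3% | 12.8 |
| Level A | 204/516 | 0.30 | 0.5 | 82.4% | 90.7% | 8.3 |
| Level A | 204/322 | 0.25 | 0.5 | 57.8% | 69.6% | 11.8 |
| Level A | 204/516 | 0.25 | 0.3 | 63.9% | 67.4% | 3.5 |
| Level A | 204/322 | 0.25 | 0.3 | 55.5% | 59.4% | 3.9 |
| Level B | 180/540 | 0.31 | 0.3 | 79.6% | 81.9% | 2.3 |
| Level B | 180/540 | 0.31 | 0.5 | 77.3% | 86.4% | 9.1 |
| Level B | 204/516 | 0.31 | 0.5 | 79.6% | 89.2% | 9.6 |
| Level B | 180/540 | 0.31 | 0.7 | 77.8% | 95.1% | 17.3 |
| Level B, half with a score | 180/540 | 0.31 | 0.5 | 77.6% | 82.4% | 4.8 |
| Change | 204/516 | 0.25 | 0.5 | 53.5% | 53.2% | −0.3 |
| Change | 204/322 | 0.25 | 0.5 | 42.1% | 42.2% | 0.1 |

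A second run with half the scores usable gave about 4 points; a quarter usable gave about 1.5. With no treatment effect (Level B, ρ = 0.5), rejection was 4.7% without and 4.3% with baseline. Simulation error is about one point per power figure: with 1,500 replicates, √(0.8 × 0.2/1500) = 0.010. Allowing for it, the 2.3 to 3.9 points seen at ρ = 0.3 are reported as about 2 to 5.

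**The case against.** **The list is open.** The word introducing the correlates does not close it. This stands: the plan does not name baseline CPaSS, but it does not rule it out. A reader might infer that the plan excludes baseline and so forfeits a fixed 8 or so points of power. The documents support neither part. The correlation is assumed, and the gain depends on whether classes reflect level or change.

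**Baseline may already be in the outcome.** On a literal reading of Table 1, baseline is the first trajectory point, and using it as a covariate would regress class on part of the data that define class. This stands and has to be settled first.

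**A clean score may often be missing.** Randomisation follows the baseline survey (3 and 3.2). Section 3 lists the check-in afterwards for both groups, at the visit or within 5 business days. Section 5.1.1 lists it before randomisation but allows the same delay, and 4.3 notes that study tasks have become fully remote. This stands as a limit on the gain. It does not defeat the adjustment: whether a pre-randomisation score exists is fixed at randomisation, so a missing indicator is itself a baseline variable.

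**The plan already protects the comparison.** Randomisation is stratified by age group and qualifying behaviour, and 6.2 adjusts for covariates that differ significantly. Stratification does limit chance imbalance, so it would be wrong to say that baseline differences pass straight into the result. Adjustment triggered by a balance test does not commit the plan to this covariate.

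**Aim 1's limit on adjustment is deliberate.** It is, but it concerns joint models of several follow-ups. Aim 2 has one class per caregiver.

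**Unadjusted odds ratios nearer 1 are not biased.** Correct: marginal and conditional odds ratios are different estimands. A reader might infer that the unadjusted test is invalid; its 4.7% rejection under no effect shows otherwise. The argument is about power and prespecification.

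**Conclusion.** The concern holds as a gap in specification with a likely but uncertain cost in power. If classes largely reflect CPaSS level, prespecified adjustment at an assumed correlation of 0.5 adds roughly 8 to 13 points with a score for everyone and about 4 to 5 if half have one. At 0.3 with full scores it adds about 2 to 5. If treatment acts only on change unrelated to baseline, it adds about 0 and costs almost nothing.

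These figures rest on an assumed correlation, assumed shares with usable scores, classes treated as known, and basic and enhanced TCBD combined although Aim 2 hypothesises three conditions. Because most of the plan calls the trajectory secondary, the point deserves a change but does not threaten the main efficacy result in Aim 1.

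**What to change.** In 6.2, Aim 2:
1. State that baseline CPaSS is not part of the modelled trajectory, and bring Table 1 (3.3) into line with 3.2 and 3.4.1.
2. Add baseline CPaSS as a prespecified covariate in the multinomial model, beside treatment group, race/ethnicity and child age group. Use only scores taken before both randomisation and counselling, with a missing indicator for everyone else.
3. Make the baseline-adjusted treatment odds ratios the main treatment result for this secondary outcome, with the unadjusted ones as supportive.

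The cost is a few sentences and, for each non-reference class, one parameter for the score and one for the missing indicator. No new assessment is needed. The main estimate becomes a conditional odds ratio, and the gain shrinks if many check-ins follow randomisation.

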## 7 Safety and Adverse Events

[name] will be responsible for reporting Adverse Events and Other Reportable Information and Occurrences to the Lurie Children's Hospital IRB and the Project Officer for this grant as required and as applicable to the study protocol. The timing of reporting of an adverse event by [name]

# Emergency Medicine Prospective Protocol

will be dependent on the severity of the event and whether the adverse event was expected (included in the informed consent).

## 7.1.1 Data and Safety Monitoring Plan

The Principal Investigator, [name] will be responsible for the data safety and quality in this low risk trial of a behavioral intervention to promote correct and consistent size-appropriate child passenger safety behaviors. It should be noted that all research project involving human participants at Ann & Robert H. Lurie Children's Hospital of Chicago, including the proposed one, require approvals from the Lurie Children's Hospital Institutional Review Board. In addition, because of the potential for sensitive data collection using digital photographs, a Certificate of Confidentiality will be obtained for this study from The Eunice Kennedy Shriver National Institute of Child Health and Human Development.

[name] will ensure that all relevant IRB policies, procedures and stipulations are followed. She will be responsible for ensuring that other investigators and project staff adhere to IRB policies including (1) All participants will understand, agree to and sign a written consent forms before participating; (2) strict adherence to a participant's right to withdraw or refuse to answer questions will be maintained; (3) the questionnaires will be confidential and no names will be associated with the survey data; (4) consent forms and identifying information will be kept separate from the participants' study data; (5) all identifying information in digital form (e.g., follow-up tracking data) will be encrypted and saved on password-protected devices and stored in a locked filing cabinet. All identifying information on paper (e.g., consent documents) will be stored in a locked filing cabinet. Computers using de-identified data for analysis will be password protected; and (6) participants will be informed in the consent form with information to contact the PI, the project manager, and the IRB office with any questions and/or concerns. [name] will be responsible for submitting any amendments to the IRB before making changes to the study protocol.

[name] will be responsible for providing training to all research staff conducting assessments regarding procedures for managing anticipated issues. Specifically, this training will include information regarding warning signs of distress that occur as a result of the surveys and the means for addressing such issues and minimizing distress. Staff will receive training from [name] in management procedures if a caregiver reveals child abuse/neglect or concerns about safety. Staff training will include review of the study protocol regarding the limits of confidentiality, liaison with ED staff (i.e., clinical care providers) regarding concerns, and circumstances in which it may be necessary to report suspected child abuse or neglect to the Illinois Department of Children and Family Services (DCFS). Study procedures will also require staff to immediately contact [name] in cases where these concerns arise. [name] will be responsible for training in Motivational Interviewing (MI) techniques. The project manager will facilitate monitoring for fidelity to the intervention throughout the course of the study by reviewing and scoring audio recordings from MI sessions. A consultant with mastery of MI techniques and teaching of MI will provide feedback and additional training as needed.

The digital photographs submitted by caregivers will be reviewed by a trained research assistant within 24-48 hours of the submission. The research assistant will score the photographs with the Child Passenger Safety Score and determine which feedback messages will be returned to the caregivers in the intervention group. For the development of the CPaSS Tool, in collaboration with [name] and child passenger safety technicians, [name] has developed a list of child passenger safety behaviors that constitute serious misuse (for example, having a car seat sitting on the vehicle seat but not attached in any way). To offer greater protection in a crash to all children involved in the study whose caregivers have not obtained a size-appropriate child restraint system at the 6- or 12-month follow-up assessment, we have budgeted to provide size-appropriate

